7.1.2. First Sensitivity Analysis of the Primary Efficacy Endpoint

The first sensitivity analysis of the primary efficacy endpoint is based on the mITT population but MI for monotone missing data due to ICE2 (treatment discontinuation due to other reasons) assuming MNAR will be implemented. Otherwise the definitions of the intercurrent events and strategies on how to deal with them are the same as for the primary estimand (Table 3).

7.1.3. Second Sensitivity Analysis of the Primary Efficacy Endpoint

The second sensitivity analysis of the primary efficacy endpoint is based on the mITT population but analyses are performed only on observed cases, i.e. no imputations are performed.

7.1.4. Supportive Sensitivity Analysis of the Primary Efficacy Endpoint

The supportive sensitivity analysis of the primary efficacy endpoint is based on the PP population and presentation as per the primary estimand is applied. The definitions of the intercurrent events are the same as for the primary estimand (Table 3).

7.2. Estimands for the Secondary, Other and Exploratory Efficacy Endpoints

The estimands framework for the primary efficacy endpoint will apply for the secondary, other and exploratory efficacy endpoints related to the secondary efficacy objective, other efficacy objectives and other exploratory efficacy objectives, for all visits up to and including Week 8. This includes the definitions of the intercurrent events (Table 3) as well as their imputation methods for all binary endpoints.

For all continuous efficacy endpoints the definitions of the intercurrent events, strategies to handle the intercurrent events and imputation methods are detailed in Table 5.

Table 5: Potential intercurrent events for continuous endpoints

Intercurrent Event	Estimand: Strategy to Deal With Intercurrent Event Within Analysis	Estimand: Assessment of Patient
ICE1: Treatment discontinuation due to treatment-related AE	Hypothetical	Available data occurring on or after the ICE will be not be used for the analysis and set to

		missing. Monotone missing data will be imputed assuming MNAR.
ICE2: Treatment discontinuation due to any other reason than treatment-related AE or death	Treatment policy strategy	Available data occurring on or after the ICE will be used for the analysis as observed. Monotone missing data will be imputed assuming MAR
ICE3: Prohibited rescue treatments or rescue procedures initiation during the 8 week study treatment administration period	Hypothetical	Available data occurring on or after the ICE will be not be used for the analysis and set to missing. Monotone missing data will be imputed assuming MNAR.
ICE4: Death	Composite	Worst-case data imputation, i.e., BCDVA worst value in surviving patients

Patients who discontinue due to treatment-related AEs (ICE1) will be assumed to confound the estimate of the treatment effect and therefore is assumed have a similar outcome over time as the vehicle group under a hypothetical setting. Therefore assessments after treatment discontinuation due to treatment-related AEs will be set to missing (if not already missing) and will be imputed under the MNAR assumption using a control-based pattern approach with vehicle group as reference and randomisation strata (NK stage and region) included.

For patients discontinuing study treatment because of any reason other than treatment-related AEs and death (ICE2), a non-confounded estimate of the treatment effect is provided. Therefore the treatment policy strategy will be applied and any missing assessment will be imputed by MI assuming MAR. Patients will be imputed based on their treatment group and randomization strata (NK stage and region).

For patients who start rescue treatments or rescue procedures during the planned 8 week study treatment administration period used for treatment of NK (ICE3), a confounded estimate of the treatment effect is assumed. Therefore the estimand allows for the assessment of the treatment effect in a hypothetical setting, assuming a similar outcome over time, as expected under vehicle administration. Assessments after the start of the rescue treatments or rescue procedures will be set to missing (if not already missing) and will be imputed under the assumption of MNAR using a control-based pattern approach with the vehicle group as reference and randomisation strata (NK stage and region) included.

In case of treatment discontinuation due to death (ICE4) a composite strategy will be applied where the subsequently missing efficacy assessment will be imputed with the worst value single imputation approach, regardless of treatment group or randomisation strata (NK stage and region).

All time to event efficacy endpoints, definitions of the intercurrent events, strategies to handle the intercurrent events and imputation methods are detailed in Table 6.

Table 6: Potential intercurrent events for time to event endpoints

Intercurrent Event	Estimand: Strategy to Deal With Intercurrent Event Within Analysis	Estimand: Assessment of Patient
ICE1: Treatment discontinuation due to treatment-related AE	Composite	Available data observed on or after the occurrence of the ICE and up to week 8 (day 56) will be set to missing and imputed as failure. The patient will be censored at the end of week 8 (day 56) of the study treatment administration period.
ICE2: Treatment discontinuation due to any other reason than treatment-related AE or death	Treatment policy strategy	Available data occurring on or after the ICE will be used for the analysis as observed. Monotone missing data will be imputed using LOCF up to week 8 (day 56).
ICE3: Prohibited rescue treatments or rescue procedures initiation during the 8 week study treatment administration period	Composite	Available data observed on or after the occurrence of the ICE and up to week 8 (day 56) will be set to missing and imputed as failure. The patient will be censored at the end of week 8 (day 56) of the study treatment administration period.
ICE4: Death	Composite	All monotone missing data up to week 8 (day 56) will be imputed as failure. The patient will be censored at the end of week 8 (day 56) of the study treatment administration period.

Time to event is defined as time from treatment start to event, e.g. complete corneal healing, in days. Patients that do not have an event until end of treatment (Visit 8/Day 56) and, in case of no intercurrent event (ICE), will be censored at their last available assessment date, i.e. Visit 8 or earlier. In case ICE1 (treatment discontinuation due to treatment-related AE), ICE3 (start of rescue treatments/procedures) or ICE4 (treatment discontinuation due to death) occurred during the treatment administration period (up to Visit 8 (Day 56), the composite strategy applies where the observed values after the ICE are set to missing and imputed as failure up to Visit 8 (Day 56). If ICE2 (treatment discontinuation due to any other reasons) occurs during the treatment administration period and up to Visit 8 (Day 56), treatment policy strategy will be applied where LOCF is used to impute any monotone missing data up to Visit 8 (Day 56). The censoring date after the occurrence of an ICE and respective imputation will be the actual assessment date at Visit 8 (Day 56), if available. In case the patient has no efficacy assessment done at Visit 8 (Day 56), the censoring time (days) after the ICE occurrence will be set to Day 56 which is the last scheduled efficacy assessment day in the 8 week treatment administration period as planned per protocol.

Filing requirements: TMF

8. General Aspects for Statistical Analysis

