14.2 NRS for Ocular Symptoms and Tolerability

The NRS of ocular symptoms and tolerability will use an 11-point scale (see APPENDIX 2). The scale question will be "On average since your last visit how would you rate the following symptoms in your treated eye on the scale 0 to 10, 0 means no symptoms and 10 means the worst possible discomfort. The scale will be administered for each of the following 7 symptoms: foreign body sensation, burning/stinging, itching, ocular pain, sticky feeling, blurred vision, and photophobia."

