5.5. Other Exploratory Endpoints

- Change from baseline in QoL evaluated using the NEI VFQ-25.
- Change from baseline in the overall NRS score for ocular symptoms and tolerability.

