An ANCOVA will be performed for the change from baseline in composite score data at Week 8. The LSM estimates and 95% CIs of each treatment group, as well as the LSM differences, 95% CIs and p-values from the comparison between the REC 0/0559 groups and the vehicle group, will be reported. Missing values for the composite and subscale scores are imputed according to the estimand framework and definition of ICE of the continuous secondary and other exploratory efficacy endpoints (Section 7.2). Missing data will be imputed with MI as per Section 8.3.2. A summary table will present all values and changes from baseline in composite and subscale scores by visit and treatment group based on observed data only.

10.5.2. Other Exploratory Endpoint 2

The change from baseline in the overall NRS score for ocular symptoms and tolerability will be analyzed. The overall NRS score will be calculated as the arithmetic mean of individual symptoms scores. If more than 3 symptom scores are missing the overall NRS mean score will be set to missing for the respective visit.

An ANCOVA will be performed for the change from baseline in overall NRS score at Week 8. The LSM estimates and 95% CIs of each treatment group, as well as the LSM differences, 95% CIs and p-values from the comparison between the REC 0/0559 groups and vehicle group, will be reported. Missing values for the overall mean NRS score are are imputed according to the estimand framework and definition of ICE of the continuous secondary and other exploratory efficacy endpoints (Section 7.2). Missing data will be imputed with MI as per Section 8.3.2. A summary table will present all values and changes from baseline in each symptom score and overall score by visit and treatment group based on observed data only.

11. Analysis of Pharmacokinetics

The pharmacokinetics of MT6, the active metabolite of REC 0/0559, will be evaluated using an intense PK sampling schedule for the first 24 patients on Day 1 and Day 7. All randomised patients will have trough levels measured at Day 28 and Day 56. All outputs are presented for the patients in the PK population.

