Table 14.2.4.2.1 Change from Baseline in the Overall NRS Score for Ocular Symptoms and Tolerability at Week 8 - Other Exploratory Endpoint 2 (mITT)

Programming Note:

The layout is the same as Table 14.2.4.1.1. Present the symptom scores in subtitle. Following footnotes to be displayed:

n: Number of patients with data available, N: Number of patients within treatment group, SE: Standard Error, NRS: Numerical Rating Scale, LSM: Least Squares Mean

Note: The LSM estimates, LSM differences and 95% confidence intervals as well as the p-values are obtained from an ANCOVA with treatment as main effect and baseline value (last available value before treatment start) and randomisation strata (disease stage and region) as covariates.

Note: Multiple imputation (MI) with a Markov Chain Monte Carlo (MCMC) approach is used for any intermittent missing data. For monotone missingness up to Week 8 due to ICE1 and ICE3 assuming missing not at random (MNAR), MI is implemented with a control-based pattern approach (vehicle as reference). Observed data as collected will be used for ICE2 and MI under MAR assumption is used for any monotone missing data. Unobserved data due to ICE4 is imputed with a worst value single imputation approach.

Note: The results that are displayed in this table are combined from 20 imputed datasets according to Rubin's rules.

- [1]: Vehicle group is used as reference. For the confirmatory analysis based on the primary estimand a gate keeping procedure is applied in the following order:
- 1. REC 0/0559 5.0 µg/day vs vehicle at 0.04 alpha level and if significant, REC 0/0559 2.5 µg/day vs vehicle at 0.05 alpha level. If both tests are significant, REC 0/0559 0.5 µg/day vs vehicle is tested at 0.05 alpha level.
- 2. REC 0/0559 2.5 μ g/day vs vehicle at 0.01 alpha level and if significant, REC 0/0559 5.0 μ g/day vs vehicle at 0.05 alpha level. If both tests are significant, REC 0/0559 0.5 μ g/day vs vehicle is tested at 0.05 alpha level.

SAP Version: 1.0. 31-May-2024

Controlled Document ID: 3903A.02, Effective Date 31-Aug-2020

Sponsor: Recordati Rare Diseases; Protocol No.: REC0559-B-001

Table 14.2.4.2.2 Summary and Change from Baseline in Each Symptom Score and the Overall NRS Score for Ocular Symptoms and Tolerability by Visit - Other Exploratory Endpoint 2 (mITT)

Programming Note:

The layout is the same as Table 14.2.4.1.2. Following footnotes to be displayed:

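### The only inferential NRS tolerability comparison replaces scores after a treatment-related-AE discontinuation with vehicle-referenced values, so it can understate on-drug intolerance, and no sensitivity analysis checks it

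*SAP*

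**What the plan says.** SAP 5.5 lists "Change from baseline in the overall NRS score for ocular symptoms and tolerability" as the second of two other exploratory endpoints. Protocol 14.2 defines seven symptoms, each rated 0 to 10, and the overall score is their mean. SAP 10.5.2 plans a Week 8 ANCOVA with least squares mean differences, confidence intervals and p-values for each dose against vehicle. For missing data it points back to the general rules: "Missing values for the overall mean NRS score are are imputed according to the estimand framework and definition of ICE".

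Those rules are in SAP 7.2, Table 5. For ICE1 (stopping treatment because of a treatment-related AE) the strategy is hypothetical, and the cell reads "Available data occurring on or after the ICE will be not be used for the analysis and set to" missing. The text below the table says that "assessments after treatment discontinuation due to treatment-related AEs will be set to missing (if not already missing) and will be imputed" under MNAR, "using a control-based pattern approach with vehicle group as reference and randomisation strata (NK stage and region) included". The footnote to shell Table 14.2.4.2.1 repeats this for the NRS. For ICE2 (stopping for other reasons) Table 5 keeps the observed data.

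The discarded data will usually exist. Protocol 8.4.1 asks patients who stop study drug to keep attending visits to Day 56. The NRS question itself looks back: "On average since your last visit how would you rate the following symptoms in your treated eye".

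The sensitivity analyses in SAP 7.1.2 to 7.1.4 concern the primary endpoint only.

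**The concern.** Vehicle-referenced imputation works against the drug when the outcome is a benefit, such as BCDVA. When the outcome is whether the drops are tolerated, it works the other way: a patient who stopped because the drops caused symptoms is modelled as if on vehicle, which removes the effect of interest in the patients most likely to show it. The recall period adds to this. A score taken at the stopping visit, or at the next visit when the drug was stopped between visits, can describe days on drug and still be discarded.

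Tolerability bears on a primary objective, the choice of the dose with the best benefit-risk ratio (Protocol 6.1.1, SAP 3.1). The Week 8 ANCOVA is the only NRS analysis that yields an estimate against vehicle with an interval and a p-value.

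**Working it through.** **Arm size.** The plan's figure is 27 per arm (SAP 4.3: 27% on vehicle, a 45-point difference, hence 72%; two-sided alpha 0.05, about 80% power, 15% dropout). The usual two-proportion formula gives 19 per arm without continuity correction and 23 with it. Then 23 × 1.15 = 26.45, rounded up to 27 (dividing instead, 23/0.85 = 27.06, rounded up to 28). The stated 27 reproduces. It matters here only as the denominator.

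**Shift in an arm mean.** Let k be the ICE1 patients in an arm and d their excess NRS change over vehicle. If imputed values are fully vehicle-like, the arm mean loses (k/27) × d. Neither k nor d is in the documents, so these are assumed ranges. The value k = 4 corresponds to the whole 15% dropout estimate being ICE1 (0.15 × 27 = 4.05).

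| k | d = 1 | d = 3 | d = 5 |
|---|---|---|---|
| 1 | 0.04 | 0.11 | 0.19 |
| 2 | 0.07 | 0.22 | 0.37 |
| 4 | 0.15 | 0.44 | 0.74 |

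With k = 0 the shift is zero. Because the score is a mean of seven items, d = 3 needs 7 × 3 = 21 points in total. If only burning/stinging, itching and ocular pain worsen, that is 21/3 = 7 points each on a 0 to 10 scale. The right-hand columns are therefore demanding.

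ICE1 applies to vehicle patients as well. The shift in the difference between arms is (k_active × d_active − k_vehicle × d_vehicle)/27, which is smaller than the table if vehicle patients also stop for related AEs.

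**If the imputation uses earlier scores.** SAP 8.3.2 specifies monotone linear regression for the MNAR step but does not expressly list earlier visits as predictors. A simulation in which it does use them had 4 stoppers of 27, 3 points worse on drug and stopping at the third post-baseline visit. It assumed SD 2, a vehicle mean falling 0.2 per visit, and eight post-baseline visits (the schedule has seven to Week 8). Contributions to the active-arm mean:

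| Symptoms after stopping | On-drug excess, 4/27 × 3 | Actual Week 8 excess | Imputed, adjacent-visit correlation 0.6 | Imputed, correlation 0.9 |
|---|---|---|---|---|
| Persist (+3) | 0.44 | 0.44 | 0.03 | 0.26 |
| Partly resolve (+1) | 0.44 | 0.15 | 0.04 | 0.26 |
| Resolve (0) | 0.44 | 0.00 | 0.03 | 0.26 |

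Against on-drug tolerability, the imputed value is too small in every row. Against the patient's actual Week 8 state, it can be too small or too large.

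**Recall and wording.** The Table 5 cell discards data *on or after* the event; the sentence below it says *after*. NRS visits fall on Days 3, 7, 14, 21, 28, 42 and 56. Under the cell's wording, a patient who stops on or before Day 3 contributes no on-drug score to the ANCOVA. Under either wording, a patient who stops between Day 28 and Day 42 loses the Day 42 score, although its recall runs back to Day 28 and so includes on-drug days.

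**The case against.** A reader might infer that intolerance on the active doses will be hidden. The documents do not support that. SAP 10.5.2 and shell Table 14.2.4.2.2 give each symptom and the overall score by visit and arm on observed data. Listing 16.2.6.7 shows patients' NRS results by visit. SAP 12.1 tabulates related TEAEs and TEAEs leading to drug discontinuation by arm. The layout reused for the NRS ANCOVA table prints ICE1 counts. Scores before the event are also kept.

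A reader might also infer that the distortion always favours the drug. That depends on the target. If Week 8 symptoms after stopping are of interest and they resolve off drug, the simulated rule overstates intolerance. Some of the seven items, such as foreign body sensation, blurred vision and photophobia, can reflect the disease. The SAP handles the NRS with the exploratory efficacy endpoints, and if the drug relieves symptoms a vehicle reference is cautious.

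Nor is ICE1 drug intolerance by definition. Protocol 12.7.1 counts an AE as related when drug involvement cannot be ruled out, and the event need not be ocular.

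Finally, the endpoint is exploratory and no section ties dose selection to its p-value.

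All of this stands and limits the point. It does not remove it: the one inferential NRS analysis uses an assumption unsuited to a tolerability reading, discards data that the protocol works to collect, and has no alternative analysis beside it. The descriptive outputs reveal the problem but do not give a corrected estimate.

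**Conclusion.** The Week 8 NRS ANCOVA can understate on-drug intolerance in the active arms, and nothing planned tests how much. The size cannot be derived from the documents. Under fully vehicle-like imputation and no vehicle stoppers it is 0.04 to 0.74 points on the 0 to 10 scale for 1 to 4 stoppers and an excess of 1 to 5 points, less if the imputation model uses earlier scores, and zero if there are no ICE1 cases. The claim of understatement takes on-drug tolerability as the target; for off-drug status at Week 8 the direction is open. This is a cheap improvement to an exploratory analysis. It does not affect the primary endpoint, and it does not mean that intolerance would go unreported.

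**What to change.** Before unmasking, amend SAP 7.2 and 10.5.2 and add a table beside 14.2.4.2.1:

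- Pre-specify a supplementary NRS ANCOVA that does not use vehicle-based imputation for ICE1 and keeps the observed post-ICE1 scores (treatment policy, as Table 5 does for ICE2).
- Accompany it with a while-on-treatment comparison using the last score whose recall period covers on-drug days. This captures symptoms that resolve on stopping, which the first analysis would miss. It should stand beside the Week 8 analyses and not replace them, because an early score from a stopper would be set against Week 8 scores from completers.
- State that, for the NRS, a score recorded at the stopping visit counts as on-drug. This also settles *on or after* against *after* in SAP 7.2.
- Keep Table 5 as it is for BCDVA.

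The cost is one or two extra analyses and a derivation rule, with no new data. Active arms may look slightly worse on the NRS.

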8.4.1 Withdrawal from Study Drug

Patients permanently withdrawn from study drug should not be withdrawn from the study and, apart from study drug administration, should continue all scheduled study visits and procedures until the end of the scheduled treatment period at Day 56/Visit 8 (±3 days) to ensure complete follow-up (except in cases where the patient has withdrawn consent for study participation). The Follow-up Visit should take place 4 weeks after Day 56/Visit 8 (±3 days) regardless the date of definitive study drug discontinuation. If this is not possible, patients will be at least asked to return to the study site as soon as possible to complete the Early Termination and Follow-up Visit assessments as indicated in the Schedule of Assessments (Table 2).

If a patient discontinues study drug for any reason, the study site must immediately notify the medical monitor. The date and the reason for discontinuation must be recorded on the electronic case report form (eCRF).

In the event that a patient discontinues study drug prematurely because of a treatment-emergent adverse event (TEAE) or serious TEAE, the TEAE or serious TEAE will be followed up until it resolves (returns to normal or baseline values) or stabilises, or until it is judged by the investigator to no longer be clinically significant.

A patient may be withdrawn from the study drug at any time for reasons including, but not limited to, the following:

- Progressive disease: A rescue treatment may be initiated by the investigator according to clinical judgment as described in Section 9.6.2.
- Unacceptable toxicity or AE
- General or specific changes in the patient's condition that renders him/her ineligible for further treatment according to the inclusion/exclusion criteria (eg, suspected hypersensitivity to the study drug, pregnancy, etc)

Corneal healing is not a reason that study drug should be withdrawn before the end of the 8-week treatment period.

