4.3. Determination of Sample Size

A total of 108 patients will be randomly assigned to 1 of the 3 active treatment arms or the vehicle treatment arm (27 patients per arm). Randomisation will be stratified by disease stage (Stage 2, Stage 3) and region (Europe, North America).

Considering an estimated response rate of 27% for the vehicle treatment arm based on studies conducted in a similar patient population with cenegermin (Oxervate) and with approximately 80% of power and a 2-sided alpha of 0.05, the sample size of 27 patients per group (including a 15% estimate of dropout rate) should allow analysis to show a difference of at least 45% between the active treatment arms and the vehicle treatment arm.

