9.7. Treatment Compliance

Patients will be instructed to bring their unused/partially used/empty containers back for inspection at each study visit, and the number of opened BFS containers will be recorded. Patients will also be instructed to fill out a paper diary recording the date and time of study drug administration, which should be brought to the site at each study visit and reviewed with the patient. Patient compliance with the treatment will be assessed overall.

Overall compliance will be assessed by number of opened BFS containers. Noncompliance is defined as taking less than 80% or more than 120% of study drug during any outpatient evaluation period. Discontinuation of treatment for noncompliance is at the investigator's discretion and is to be noted on the eCRF.

Overall compliance (%) = (Number of used BFS containers) / [4 * (number of BFS to be used based on actual number of days of treatment)] * 100

With actual number of days of treatment calculated as:

Actual number of days = (last treatment administration date) - (first treatment administration date) + 1

Overall compliance will be summarised in a table by treatment group and overall based on the SAF population, and all data will be presented in a by-patient listing.

10. Efficacy

The analysis of all efficacy endpoints will be performed for the mITT population. Tertiary sensitivity analyses of the primary efficacy endpoint will also be performed on the PP population. The vehicle group will be used as reference group for all statistical tests.

All categorical endpoints will be analysed using the Cochran-Mantel-Haenszel (CMH) test stratified by region at randomisation as well as NK stage at randomisation. SAS procedure proc freq will be used.

All time-to-event endpoints will be evaluated by means of Kaplan-Meier (Kaplan & Meier 1958) survival analysis using a log-rank test. The Cox's proportional hazard model is used to estimate the hazard ratios, 95% confidence limits and p-values and includes covariates such as treatment group and randomisation strata, i.e. NK stage and region. SAS procedure proc lifetest will be used for the Kaplan-Meier analysis and proc phreg will be used for the Cox model.

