The time to complete corneal healing of PED or corneal ulcer is defined as the time from treatment start to no corneal fluorescein staining in the area of the PED or corneal ulcer as assessed by an independent central reader in days. Treatment group and randomisation strata, disease stage and region, are used as covariates. Patients who do not achieve complete corneal healing until end of treatment (V8/D56) are censored at date of V8/D56 or last available assessment date if early terminated in case no intercurrent event (ICE) occurred. The censoring date after the occurrence of an ICE and respective imputation will be the actual assessment date at (V8/D56), if available. In case the patient has no efficacy assessment done at (V8/D56), the censoring time (days) after the ICE occurrence will be set to Day 56 which is the last scheduled efficacy assessment day in the 8 week treatment administration period as planned per protocol. The analysis will be performed on the mITT population according to the estimand framework and ICE definitions for the time to event endpoints (Section 7.2). Missing data will be imputed with single value imputation as per Section 8.3.2.

The hazard ratios (HRs) and their 95% Wald CIs and p-values, as well as the estimate and 95% CI for the median, 25% and 75% quartiles of time to complete corneal healing, will be reported in a table; the survival probability for the treatment groups will be plotted in a figure.

10.3.4. Secondary Efficacy Endpoint 4

The time to complete corneal healing of PED or corneal ulcer is defined as the time from treatment start to no corneal fluorescein staining in the area of the PED or corneal ulcer as assessed by the investigator in days. Treatment group and randomisation strata, disease stage and region are used as covariates. Patients who do not achieve complete corneal healing until end of treatment (V8/D56) are censored at date of V8/D56 or last available date if early terminated terminated in case no intercurrent event (ICE) occurred. The censoring date after the occurrence of an ICE and respective imputation will be the actual assessment

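### Time-to-event endpoints: a patient who stops drug for an unrelated reason, leaves unhealed and has no Visit 8 reading is kept at risk to Day 56 on unobserved follow-up, and no planned analysis tests this

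*SAP*

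**What the plan says.** SAP section 7.2, Table 6, puts ICE2 under a treatment policy strategy: later readings are used where they exist, and then "Monotone missing data will be imputed using LOCF up to week 8 (day 56". The text below the table repeats this: "treatment policy strategy will be applied where LOCF is used to impute any monotone missing data up to Visit 8 (Day 56". SAP 10.3.3 adds that, when there is no Visit 8 reading, "the censoring time (days) after the ICE occurrence will be set to Day 56". The same wording recurs in 10.3.4, 10.4.4 to 10.4.7 and the table shells.

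Patients without an event and without an intercurrent event follow another rule. In 7.2 they "will be censored at their last available assessment date, i.e. Visit 8 or earlier", and 10.3.3 uses the "last available assessment date if early terminated in case no intercurrent event (ICE) occurred".

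For continuous endpoints, Table 5 imputes missing ICE2 data under a missing-at-random assumption. The sensitivity analyses in 7.1.2 to 7.1.4 concern only the primary binary endpoint. In SAP section 10, "The Cox's proportional hazard model is used to estimate the hazard ratios, 95% confidence limits and p-values".

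Protocol 8.4.1 limits how many patients are affected: those who stop drug "should continue all scheduled study visits and procedures until the end of the scheduled treatment period", unless they withdraw consent.

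**The concern.** Healing can be recorded only when the eye is examined. Take a patient last read unhealed on Day 14 who leaves the next day for a reason unrelated to drug or death and never attends Visit 8. The SAP keeps this patient in the risk set to Day 56, which adds 56 − 14 = 42 days with no examination. The patient can no longer become an event, so estimated healing is at or below the truth. It equals the truth only if no such patient would have healed by Day 56.

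The treatment policy label does not cover this. That strategy uses the outcome after stopping drug, and here no outcome was seen. A patient who leaves before Day 56 has normally stopped drug too, so most early leavers with no composite event fall under this rule rather than under last-assessment censoring.

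Time to complete healing, by central reading and by the investigator, is secondary endpoints 3 and 4 in the SAP's testing order. Protocol 7.2 gives faster healing as one reason for including the highest dose.

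**Working it through.** **Inputs from the documents.** SAP 4.3 gives "an estimated response rate of 27% for the vehicle treatment arm", a difference of 45 points (so 72% on active), two-sided alpha 0.05, 80% power, and 27 per arm including 15% dropout. Visits with fluorescein readings are on Days 3, 7, 14, 21, 28, 42 and 56.

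**Assumptions (not in the documents).** Constant healing hazard; leaving independent of healing; leaving times uniform over Days 0 to 56; dropout by arm as stated in each row below. Giving all 15% to ICE2 leavers is an upper case.

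**1. The plan's own figure.** It belongs to the binary endpoint; none is given for time to event. With the pooled formula, n = [1.96·√(2·0.495·0.505) + 0.8416·√(0.27·0.73 + 0.72·0.28)]² / 0.45² = (1.3859 + 0.5314)² / 0.2025 = 18.15. With continuity correction, n = (18.15/4)·[1 + √(1 + 4/(18.15·0.45))]² = 22.4, so 23. Then 23/0.85 = 27.06, which agrees with 27 by rounding.

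**2. Kaplan-Meier healing under the Day 56 rule.** With everyone unhealed censored at Day 56, the estimate is the simple proportion seen to heal: (1 − d)·p + d·m. Here p is true healing by Day 56, d is dropout, and m is the mean probability of being read healed by the last visit before leaving. With F(t) = 1 − (1 − p)^(t/56),

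m = [3·0 + 4·F(3) + 7·F(7) + 7·F(14) + 7·F(21) + 14·F(28) + 14·F(42)] / 56.

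- Vehicle, p = 0.27: m = 0.118. Estimate 0.85·0.27 + 0.15·0.118 = 24.7%.
- Active, p = 0.72: m = 0.376. Estimate 0.85·0.72 + 0.15·0.376 = 66.8%.
- At 5% dropout: 0.95·0.27 + 0.05·0.118 = 26.2%, and 0.95·0.72 + 0.05·0.376 = 70.3%.

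If every leaver also had an Early Termination reading on the day of leaving, m becomes 1 − p/(−ln(1 − p)). That is 1 − 0.27/0.3147 = 0.142 for vehicle and 1 − 0.72/1.2730 = 0.434 for active, giving 25.1% and 67.7%. The shortfall narrows slightly and remains.

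**3. Cox hazard ratio** (simulation, 40,000 per arm, Efron ties, treatment only). The closed-form value at 27% and 72% is ln(0.28)/ln(0.73) = 4.05; the simulated value without dropout is 4.07.

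| True healing, active | Dropout active / vehicle | HR, Day 56 rule | HR, last-reading censoring |
|---|---|---|---|
| 72% | 15% / 15% | 3.90 | 4.03 |
| 72% | 25% / 5% | 3.34 | 4.01 |
| 72% | 5% / 25% | 4.54 | 4.06 |
| 50% | 15% / 15% | 2.18 | 2.21 |
| 50% | 25% / 5% | 1.86 | 2.17 |
| 50% | 5% / 25% | 2.54 | 2.23 |
| 27% (no effect) | 15% / 15% | 1.00 | 1.00 |
| 27% (no effect) | 25% / 5% | 0.87 | 1.00 |
| 27% (no effect) | 5% / 25% | 1.13 | 0.99 |

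At 5% dropout in each arm (72% versus 27%), the ratio moves from 4.06 to 4.01. The last two rows are the same case with the arms swapped, so their expected values are reciprocals. A separate run gave 0.88 and 1.17, so about 0.88 and 1.15 is a fair summary.

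**4. If stopping drug lowers later healing.** Suppose active leavers then heal at the vehicle rate (100,000 per arm; again an assumption).

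| Dropout active / vehicle | True HR | Day 56 rule | Last-reading censoring |
|---|---|---|---|
| 15% / 15% | 3.73 | 3.88 | 4.02 |
| 25% / 5% | 3.63 | 3.41 | 4.08 |
| 5% / 25% | 3.91 | 4.49 | 3.99 |

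The Day 56 rule is nearer in the first two cases and last-reading censoring in the third. In the first case true active healing is 69.1%; the rules give 66.8% and 72.0%.

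**The case against.** The strongest defence is that last-reading censoring is not neutral. It gives leavers the later healing rate of those who stayed, most of them still on drug, which is closer to a hypothetical estimand than to treatment policy. Step 4 shows that it can then overstate the drug's benefit. This stands, and is why both versions need reporting.

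The present rule also fits other choices in the plan. LOCF for ICE2 is used for the primary endpoint (Table 3), and a leaver who is treated elsewhere resembles a rescue case, which counts as failure. So the rule looks deliberate. That does not make it observed follow-up, and it remains untested for these endpoints.

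The size is limited. The 15% is not split by cause, and part may be related adverse events, rescue or death, which have their own rules. Patients who stop drug are asked to keep attending. Fifteen percent of 27 is about four patients per arm. Only complete healing was calculated; the 20% and 50% reduction endpoints should be reached earlier, leaving fewer patients affected.

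A reader might infer that leavers go unexamined or that last-assessment censoring is a dead letter. The documents support neither: the Early Termination visit includes a fluorescein test and photograph, and a patient who finishes drug but misses Visit 8 has no intercurrent event and is censored at the last assessment.

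**Conclusion.** The point holds. For an ICE2 patient who leaves unhealed without a Visit 8 reading, the time between the last reading and Day 56 is not observed. The handling differs from the SAP's own rules for patients without an intercurrent event and for continuous endpoints, and no planned analysis shows its effect.

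The direction for Kaplan-Meier healing follows from the rule: at or below the truth. The size rests on assumptions. It is about 2 points on vehicle and 5 on active if all 15% are such leavers and leaving is unrelated to healing, and less otherwise. The hazard ratio is nearly unaffected by equal dropout and moves toward the arm with less dropout when dropout differs.

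A reader might go on to infer that the planned hazard ratios are biased for or against the drug. The documents do not support that, because they give no dropout by arm and the 25% versus 5% split is illustrative. Nor do they show that last-reading censoring gives the true value; it does so only under non-informative leaving. The primary endpoint is not touched. Secondary endpoints enter formal testing only if all three doses succeed on the primary (SAP 10.3), so this is worth correcting but does not threaten the main conclusion.

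**What to change.** In SAP Table 6, the text below it, 10.3.3 to 10.3.4, 10.4.4 to 10.4.7 and the matching shells, change ICE2 only: use every observed reading, including the Early Termination visit, and if the patient has had no event, censor at the last efficacy assessment up to Visit 8. Keep the Day 56 LOCF version as a prespecified sensitivity analysis and report the two together, with ICE2 leavers counted by arm. Leave ICE1, ICE3 and ICE4 as they are.

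Also reconcile the note to Listing 16.2.6.4. It names ICE1, ICE2 and ICE4 as imputed failures and then assigns LOCF to ICE2, whereas section 7.2 names ICE1, ICE3 and ICE4.

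The cost is SAP wording, one derivation line in the time-to-event dataset and a second set of outputs, with no change to data collection. The downside is that the main curves would rely on non-informative censoring for ICE2 leavers and would overstate healing if those patients would have healed less than the patients who stayed. The retained Day 56 version shows how much that matters.
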